## **5. Treatment**

All patients admitted with a diagnosis of TBM will be treated with standard regimen, four anti-tuberculous drugs for 6 months and prednisone (2mg/kg body weight; maximum dose 60mg daily) for the first month of treatment. All patients with ventriculomegaly on computed tomography will undergo an air encephalogram. Children with non-communicating hydrocephalus will undergo immediate ventriculoperitoneal (VP) shunting. Response to treatment will be monitored clinically and by a repeat CT scan of the brain after the first month of treatment.

All patients admitted with a diagnosis of bacterial meningitis will be treated with standard regimen third generation cephalosporin. Viral meningitis will be treated symptomatically; cases of suspected or proven herpes encephalitis will be treated with acyclovir. All HIV co-infected patients will be offered antiretroviral therapy (ART). Patients treated for TBM will only be started on ART after 4-6 weeks of anti-tuberculous therapy to minimize the risk of immune reconstitution inflammatory syndrome (IRIS). An exception will be made in cases who are severely immune-suppressed; they may be started on ART immediately. ART will consist of first-line therapy (for drugs & dosages per kg see addendum 2). Baseline CD4 counts and viral loads will be done before initiation of ART and repeated at 6 monthly intervals.

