**Literature review**

**Introduction**

Tuberculous meningitis (TBM) is the most common type of bacterial meningitis in the Western Cape Province (WCP) of South Africa . The tuberculosis (TB) incidence in South Africa has risen from 301 new cases/100,000 population in 1990 to 948 new cases/100,000 population in 2007 , and although the world-wide incidence of the disease has fallen by an average of 1.5% per year since 2000, the incidence of the disease in South Africa is still 834 per 100, 000 population as indicated by recent World Health Organization (WHO) reports . The TB burden is worsened by the human immunodeficiency virus (HIV) pandemic. TBM represents the most severe manifestation of TB with high morbidity and mortality, despite adequate anti-TB therapy. This is mainly the result of delayed diagnosis and initiation of appropriate therapy . The pathogenesis of TB is still poorly understood. Despite ongoing research, early, cost-effective diagnostic tools are lacking . Demonstration of acid-fast bacilli and/or culture of *Mycobacterium tuberculosis* (*Mtb*) from cerebrospinal fluid (CSF) represents the gold standard for diagnosing TBM, but unfortunately the sensitivity of both these tests is low . The sensitivity of the recently developed GeneXpert

test (Cepheid Inc., USA) for TBM is ~50-60%, but only improves to 72% when CSF is centrifuged as demonstrated in a recent study . The diagnosis of TBM is therefore based on a combination of clinical, laboratory and radiological findings. However, a clinical diagnosis is often delayed, especially in the early stages of the disease when few neurological signs may be present. In addition, the CSF picture can be highly variable . Although various case definitions for TBM have been reported in the literature, diagnostic criteria vary widely, so that no standardized case definition exists . An international workshop on TBM was held during May 2009 in Cape Town, South Africa. This was attended by international experts on TBM, and a uniform case definition for TBM was proposed for future research.

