### **Uniform research case definition for TBM **

It is proposed that patients suspected of having TBM be categorized into definite, probable, possible and no TBM. This is proposed to obtain standardization for research purposes, for adults and children, and was not primarily devised as a clinical tool. The clinical diagnosis of TBM (probable or possible) is based on clinical findings and special investigations (Table 1). The boundaries between groups are not fixed, and patients can interchange between groups, based on results of laboratory and radiological investigations. Definite TBM requires demonstration of acid-fast bacilli in the CSF, *Mycobacterium tuberculosis* culture from CSF, a positive nucleic acid amplification test (PCR) of CSF or histopathological evidence of *Mycobacterium tuberculosis* from a central nervous system site.

Patients must have a clinical diagnosis of meningitis including one or more of the following symptoms: headache, irritability, vomiting, fever and neck stiffness (Table 1). The diagnosis of probable or possible TBM is based on 1) clinical findings 2) CSF results 3) neuroimaging findings 4) evidence for TB outside the central nervous system and 5) additional laboratory criteria. A scoring system then determines whether a patient falls in the probable or possible TBM category (Table 1). Points are allocated for a positive finding in each of the categories, with a maximum score for each category. A total score of at least 10 is compatible with probable TBM, while a total score of at least 6 equates with a possible TBM diagnosis. A certain number of points have to come from the CSF or neuro-imaging criteria to ensure that the patient is indeed suffering from meningitis and not some other chronic type of tuberculosis. It is also suggested by the consensus

group that all patients should have additional CSF investigations to exclude alternative causes for the clinical presentation.

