#### **4. Diagnostic work-up**

All patients will undergo a comprehensive clinical evaluation (Addendum1). Routine special investigations will be performed. CT of the brain will be done in all probable TBM cases and in other cases of meningitis when indicated. Air- encephalography will be performed in all TBM cases with hydrocephalus. MR imaging will be done as clinically indicated. Lumbar puncture will be performed and the following CSF investigations performed: appearance and colour determination; differential cell count determination by standard methods; protein, glucose and chloride determination by standard methods; centrifugation with Gram stain and India ink examination of the deposit; culture of the centrifuged deposit on blood agar plates for pyogenic bacteria; Auramine “O” staining & fluorescence microscopy, culture using the BBL™MGIT(Mycobacterium Growth Indicator Tubes)™ of Becton and Dickinson and detection of *Mtb* DNA using the HAIN Genotype MTBDRplus kit. Samples will be tested using Xpert Ultra and newer technologies e.g. AlereQ TB and the Savannah MTB assay. Microbiomic analysis will be performed on microbial DNA extracted from patient specimens and sequenced on the Illumina MiSeq platform. All data will be recorded on a pre-designed clinical data capture sheet (see addendum) and entered into a computerized database. Finally, data analysis will be carried out using appropriate software and statistical packages.

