#### **The diagnosis of TBM will be made based on the following criteria:**

A diagnosis of **probable** TBM will be made if two or more of the following criteria are present in the setting of a characteristic history and CSF changes associated with TBM: A positive history of contact with an adult TB case, a positive tuberculin skin test, a chest x-ray suggestive of pulmonary tuberculosis (hilar lymphadenopathy, miliary tuberculosis or cavitation, CT or MRI demonstrating the characteristic features of TBM (ventricular dilatation, meningo-vascular enhancement and/or granuloma/s), poor weight gain or weight crossing percentiles documented on the Road to Health Card or positive identification of acid fast bacilli from gastric washings (microscopy or culture).

A diagnosis of **definite** TBM will be made if acid-fast bacilli is present in the CSF, *Mtb* is cultured

from CSF, a nucleic acid amplification test of CSF is positive or there is histopathological evidence of *Mtb* from another central nervous system site. The degree of TBM will be classified according to the proposed modified British Medical Research Council (BMRC) classification of 1948. -Stage I: Glasgow Coma Scale (GCS) of 15 and no focal neurology, Stage IIa: GCS of 15 plus focal neurology, Stage IIb: GCS of 11-14 with focal neurology, Stage III: GCS <11. All investigations required for establishing a diagnosis (TBM or no TBM) are usually done routinely and shall therefore not specifically be as part of the current study.

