collected will be kept in a separate password protected file and this will only be known to and accessed by the Clinical Principal Investigator (Prof [name]). All samples sent to the Immunology Research Laboratory shall be anonymized and only identifiable by RedCap generated bar codes. Patients/legal guardians shall be informed that their refusal to participate in the present study shall not influence their care in any way. Good clinical practice guidelines will be adhered to.

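### No date is set for the final reference diagnosis and no later check for children labelled not-TBM, so missed TBM may be analysed as control and bias accuracy in either direction

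*Combined protocol and SAP*

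**What the plan says.** All references are to the combined protocol and SAP.

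- **The risk is acknowledged.** The Introduction says that "a clinical diagnosis is often delayed, especially in the early stages of the disease when few neurological signs may be present", that CSF findings vary widely, and that smear and culture have low sensitivity. It puts GeneXpert sensitivity at about 50–60%, or 72% on centrifuged CSF.
- **Regrouping is accepted in principle.** The literature-review section on the uniform case definition says: "The boundaries between groups are not fixed, and patients can interchange between groups, based on results of laboratory and radiological investigations". The methods give no time or procedure for this.
- **Work-up differs by group.** Under 4. Diagnostic work-up, CT is planned for all probable TBM cases, and for other meningitis when indicated.
- **Follow-up differs by group.** Under 5. Treatment, the paragraph on TBM patients says: "Response to treatment will be monitored clinically and by a repeat CT scan of the brain after the first month of treatment". For the comparison groups only treatment is given, for example: "All patients admitted with a diagnosis of bacterial meningitis will be treated with standard regimen third generation cephalosporin". Children with normal CSF are not discussed there.
- **One other repeat contact exists.** For HIV co-infected patients: "Baseline CD4 counts and viral loads will be done before initiation of ART and repeated at 6 monthly intervals". It is tied to antiretroviral therapy, not to the meningitis diagnosis, and is not a check for TBM.
- **Analysis groups.** The statistical section compares participants with TBM against those without it. It has no rule for uncertain or changed diagnoses.

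**The concern.** In a diagnostic accuracy study, every child's reference label must be as reliable as the design can make it, and equally so in both groups. Here a negative work-up at presentation does not exclude TBM, by the protocol's own account of the tests. The children in whom a missed case would be found have less imaging and no stated later look. A child whose TBM declares itself after the label has been used would remain in the control group.

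Aim 1 is to validate an existing three-marker CSF signature, so its sensitivity and specificity are the main product. Misclassified controls shift both, and neither a larger sample nor a confidence interval reveals the shift. The same labels also train and test any new signature under aims 2 and 3.

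**Working it through.** The plan gives no figure on this point and no rate of missed TBM, so there is nothing to reproduce. The calculation below is an illustration over an assumed range.

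**Inputs**
- TBM cases: 72, stated as a minimum. Total: 460, stated as a maximum (3. Inclusion and exclusion criteria).
- Controls: at most 460 − 72 = 388.
- Pilot accuracy of the three-marker signature: sensitivity Se = 52%, specificity Sp = 95% (Use of host biomarkers in the diagnosis of TBM).
- f = share of labelled controls who really have TBM. This is assumed at 1% to 10%.
- d = share of those missed children whom the signature detects. It is unknown, so two cases are shown.

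**Formulas**
- Apparent specificity = (1 − f) × Sp + f × (1 − d).
- True sensitivity when the labelled cases show 52% = (72 × 0.52 + 388 × f × d) / (72 + 388 × f).

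**Case A: missed children are detected at the same 52%.** True sensitivity stays at 52%. At f = 5%, apparent specificity = 0.95 × 0.95 + 0.05 × 0.48 = 0.9025 + 0.0240 = 92.65%. Each 1% of missed TBM costs 0.95 − 0.48 = 0.47 points.

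**Case B: none of the missed children is detected.** At f = 5%, apparent specificity = 0.9025 + 0.05 = 95.25%. True sensitivity = 37.44 / (72 + 19.4) = 41.0%.

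| f | Children (388 × f) | A: apparent specificity | B: apparent specificity | B: true sensitivity behind an apparent 52% |
|---|---|---|---|---|
| 1% | 3.9 | 94.5% | 95.05% | 49.3% |
| 2% | 7.8 | 94.1% | 95.1% | 46.9% |
| 5% | 19.4 | 92.65% | 95.25% | 41.0% |
| 10% | 38.8 | 90.3% | 95.5% | 33.8% |

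**Direction.** Apparent specificity is unbiased only if 1 − d = Sp, that is d = 5%. Above that it is understated, below it slightly overstated. Sensitivity is overstated whenever d is below 52%.

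**Predictive value in the 72:388 mix, case A, f = 5%.** Without error: 37.44 / (37.44 + 388 × 0.05) = 65.9%. With error: 37.44 / (37.44 + 388 × 0.0735) = 56.8%.

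**Against sampling error.** The 95% half-width for specificity is 1.96 × √(0.95 × 0.05 / 388) = 2.2 points. The case A loss reaches this at f of about 4.6% (2.17 / 0.47).

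**The case against.** **The bias is small and its rate has no source.** This is largely right. No missed rate can be taken from the documents, 388 controls is a ceiling, and in case A the loss of specificity stays within sampling error until about 4.6% of controls are missed cases. It is also right that one cannot simply say specificity is understated, because case B goes the other way. What remains is that the plan offers no means of learning which case applies, or how many children are involved.

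**The information may be elsewhere.** The consent pages were removed, and the clinical evaluation form and data capture sheet are not in the text. A final diagnosis or outcome could be recorded there. Even so, a date for fixing the label and a rule for changing it belong in the methods, and they are not there.

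**A reader might infer more: that not-TBM children are never seen again, that late positives cannot reach the clinician, and that missed children go untreated.** The documents do not support this.
- The tests that establish the diagnosis belong to ordinary care: "All investigations required for establishing a diagnosis (TBM or no TBM) are usually done routinely".
- The definition of definite TBM puts no time limit on a positive CSF culture or nucleic acid test, and nothing bars treatment after a later diagnosis.
- The coding sentence is limited: "All samples sent to the Immunology Research Laboratory shall be anonymized and only identifiable by RedCap generated bar codes". The work described for that laboratory is host biomarkers, flow cytometry and host RNA, with no detection of the organism. Bar codes, and a data file held by the clinical principal investigator, leave re-linking possible.
- HIV co-infected children do have six-monthly contact, whatever their meningitis diagnosis.

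Silence on a step is not a prohibition of it. What is left on reporting is a gap in wording. The work-up section says "Samples will be tested using Xpert Ultra and newer technologies e.g. AlereQ TB and the Savannah MTB assay" and adds microbial sequencing, but not where these are run or how a positive is reported.

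**Conclusion.** The point holds as a gap in the reference standard. The plan names the difficulty of recognising early TBM and accepts that children may change group, yet sets no time for the final diagnosis and no later outcome check for children labelled not-TBM. The more thorough imaging and the one-month check go mainly to the TBM group. Some missed TBM may therefore be analysed as control.

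The size rests wholly on the assumed missed share and on how the signature behaves in those children. At 5% of 388 controls, the result lies between a specificity 2.35 points too low and a sensitivity about 11 points too high (52% against 41%). At 1% the figures are about 0.5 and 2.7 points. The first figure takes detection at 52%, the second no detection. A single direction of bias is not established, nor is any failure of care. The change is worth making because it is cheap and protects the main estimates. The reporting of newer assays is a secondary matter of wording.

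**What to change.** 1. State that the reference label is locked only after CSF culture is final and after one check, at a fixed time such as 3 months, of hospital, laboratory and TB-treatment records for every child labelled not-TBM.
2. Have the check and any re-labelling done without sight of biomarker results. Re-label children found to have had TBM at enrolment.
3. Report accuracy with and without the re-labelled children. In this high-incidence setting, some later diagnoses may be new disease rather than TBM missed at enrolment.
4. As wording only, state where the newer *Mtb* assays and microbial sequencing are run and how positives are reported. The documents give no accuracy on CSF for the newer technologies named as examples (AlereQ TB and the Savannah MTB assay), so the text should allow for false positives. No clinical rule is proposed here.

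**Cost.** Protocol wording and one records check per control child, with no added visit or procedure. Labels lock a few months later, the checking takes staff time, and records may miss children treated elsewhere. The check therefore removes the bias only as far as it finds the missed cases.

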## **Collection and processing of samples for the proposed study**

All samples required for the current study shall be collected during specimen collection for routine diagnosis. That is, specimens shall not specifically be collected from any study participant solely for the purposes of this study. During the collection of samples (CSF and whole blood) for routine clinical investigations, the alcohol swab used to sterilize the puncture site will be collected and

used to subtract background DNA found on the skin, during sequence analysis for the microbiome aspects of the study (aim 4). About 5 mL of CSF (3-7ml would be aimed for dependent on age and ease of lumbar puncture), shall be collected into sterile cryo tubes (Greiner bio-one) for use for research purposes, depending on how much is left over after specimens required for routine diagnosis have been collected. It must be stressed that although it is known that collection of up to 10ml of CSF in children with TBM may be beneficial in relieving of the pressure on the brain, hence help with alleviation of the symptoms, the amount of CSF collected will depend on the age, clinical presentation of the child, and whether collection of the specimen (3 to 7mL) will be beneficial to the child as determined by the specialist neurologist or medical practitioner treating the child. This will be followed by the collection of 1ml of whole blood into a serum blood tube and 2.5ml into a paxgene blood RNA tube, for the isolation of messenger RNA for future gene expression studies (aim 3). Furthermore, an additional 1 ml of blood will be collected from a subset of children for investigation of immune cells (whole blood intracellular staining by Flow cytometry; aim 7). Whether such an additional blood specimen is collected will depend on the judgement of the treating clinician and specialist paediatric neurologist, with the child's wellbeing always taking priority over the research. Where possible, mid-stream urine will be collected into sterile collection tubes for diagnostic analysis as part of aims 5 and 6. Therefore, depending on the judgement of the clinician and specialist paediatric neurologist, a total of up to 5mL (3 to 7ml) of extra CSF and up to 4.5ml of whole blood and up to 5 mL of urine (where possible) shall be collected from each consenting study participant for the purposes of this study. The proposed procedure (blood and CSF collection) was used in previously approved and now completed studies which provided samples for the pilot studies leading to this validation study (**HREC ref no: N11/01/006**, Principal Investigator, [name]; and **Ref no: N09/10/265**, Principal Investigator, Dr [name]).

After collection of specimens for routine diagnostic purposes, the proposed research specimens shall be collected from consenting study participants and sent to the SUN Immunology Research laboratory, Fourth Floor, Education Building, where processing of these specimens shall occur. The CSF samples shall be centrifuged, aliquoted into 250 $\mu$ l amounts and frozen at minus 80 degrees until used for biomarker analysis using the Luminex technology, as was done in the pilot study (33). If more than 1mL of CSF is available, aliquots of the CSF will be used for immune cell

analysis by flow cytometry as mentioned above. Similarly, the 1ml of blood collected into a serum tube shall be centrifuged and serum harvested and stored at minus 80 degrees until used for biomarker analysis. The additional 1ml of blood, if collected, will also be used for flow cytometry as part of a student project. For the Paxgene blood, the tubes shall be frozen and when needed for use, RNA shall be isolated using the Paxgene blood RNA isolation kit. We will then use downstream techniques including quantitative Real Time PCR or other suitable technique to look at the usefulness of the RNA blood biosignatures already described in publications such as references (34-36), and also new signatures in the diagnosis of TBM. All sample processing shall be done according to standard laboratory procedures which are currently used in the SANAS accredited SUN-IRG laboratory.

Both the CSF and urine for metabolomics, up to 2ml and 5ml respectively, will be transported to the metabolic laboratory at Northwest University in Potchefstroom for analysis of metabolites. This will be done by performing mass spectroscopy, coupled with chromatography, followed by complex data analysis. The investigations at the metabolic laboratory will be performed and interpreted by Dr [name], from the biochemistry division at Northwest University. Stellenbosch University students will use aliquots of the CSF in future for unbiased evaluation of novel protein biomarkers that may be used in the diagnosis of TBM, for optimization of the test that will be developed as part of this project or biomarkers that may guide clinical patient management.

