### **CSF diagnosis of TBM**

It has been shown in adults that the bacterial yield of *Mycobacterium tuberculosis* can be improved by obtaining larger volumes of CSF and optimizing centrifugation . Additional measures for improving sensitivity in identification of the organism include, increasing the amount of time taken with microscopy and alternative staining methods . Based on calculations of Den Hertog *et al.*, optimal CSF centrifugation in case of mycobacterium tuberculosis infection should be at a minimum speed and duration of 3200x g for 22 minutes .

Acid-fast staining is the most rapid method for the detection of mycobacteria in clinical samples. Acid-fast staining methods include the Ziehl-Nielsen (ZN) and Auramine O stains. Since CSF is sterile, as a rule, the demonstration of acid-fast bacilli in the CSF is highly suggestive of TBM. Fluorescence microscopy uses a lower power objective lens than conventional microscopy. This enables a more rapid and cost-effective assessment of the full area of a slide. A disadvantage is the possibility of false-positive results due to inorganic objects incorporating the fluorochrome dyes . Unfortunately, the use of fluorescence microscopy has been limited in resource-poor settings by the short half-life and high cost of the traditional mercury vapour lamp. Light-emitting diode (LED) technology provides a cost-efficient alternative; it is cheap, robust and has very low energy requirements .

In response to the need for more rapid diagnosis of TB and the identification of resistant strains, nucleic acid amplification tests specific for *Mtb* have been developed. In a comparative study

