between the Genotype Mycobacteria direct assay, the Gen-Probe *Mycobacterium tuberculosis* amplified direct test and the Genotype MTBDRplus for direct detection of mycobacterium tuberculosis complex in clinical samples, the Genotype MTBDRplus had the highest sensitivity (97.9%). In a study evaluating the *Mtb* complex detection rate using the Genotype MTBDRplus assay on acid-fast bacillus (AFB) smear positive sputum and PCR positive non- sputum specimens, the sensitivities were 93.8% and 77.8% respectively. For the Genotype MTBDRplus assay, the sensitivity (98.1%) and specificity (98.7%) for rifampicin resistance is very high. The accuracy for isoniazid is variable, with a lower sensitivity (84.3%) but very high specificity (99.5%). PCR is usually only done on culture. PCR on fresh CSF could potentially offer earlier confirmation of TBM diagnosis and resistance.

The GeneXpert MTB/RIF (Xpert) assay targets the rifampin resistance-associated *rpoB* gene region by heminested PCR with three specific primers and combines the sensitive detection of *M. tuberculosis* DNA and determination of rifampicin resistance using molecular beacons. Processing time is short due to automation of bacterial lysis, DNA extraction, real-time PCR amplification, and amplicon detection in a single system. High sensitivity and specificity of the Xpert assay has been shown on sputa with the assay correctly identifying 77.3% of all culture-positive specimens. Similar results are not applicable to extrapulmonary specimens, though, where the amount of mycobacterial DNA is much less. The test runs on the GeneXpert platform (Cepheid, Sunnyvale, CA) using a disposable plastic cartridge with all required reagents. Although the WHO currently recommends Xpert as an initial diagnostic test for TBM, the sensitivity of the test on CSF samples is not as high as would be obtained with sputum samples and increased to 72% when CSF was centrifuged.

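### Subtracting DNA found on the used skin swab is the only stated contamination control for the microbiome sequencing; it cannot reliably remove reagent background, and the subtraction rule is undefined

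*Combined protocol and SAP*

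**What the plan says.** All references are to the combined protocol and SAP.

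- **Section 4, Diagnostic work-up**, sets out the sequencing: "Microbiomic analysis will be performed on microbial DNA extracted from patient specimens and sequenced on the Illumina MiSeq platform".
- **Collection and processing of samples** gives the control. When CSF and whole blood are taken, "the alcohol swab used to sterilize the puncture site will be collected and" then "used to subtract background DNA found on the skin, during sequence analysis for the microbiome aspects of the study (aim 4". Whether subtraction works by presence, by an abundance threshold or by a model is not stated.
- **The same section** has two general quality statements. CSF "shall be collected into sterile cryo tubes (Greiner bio-one) for use for research purposes", and "All sample processing shall be done according to standard laboratory procedures which are currently used in the SANAS accredited SUN-IRG laboratory". Neither names a sequencing control.
- **CSF diagnosis of TBM** describes the specimen: "Since CSF is sterile, as a rule, the demonstration of acid-fast bacilli in the CSF is highly suggestive of TBM". On the sputum performance of the Xpert assay it adds: "Similar results are not applicable to extrapulmonary specimens, though, where the amount of mycobacterial DNA is much less".
- **Statistical methods and analysis plan** covers host biomarkers, biosignatures and flow cytometry. It has no microbiome analysis.
- **Aims** lists five aims, none of which mentions the microbiome. Listed aim 4 concerns immune profiles in CSF and blood.

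**The concern.** When a specimen holds little microbial DNA, DNA introduced by the extraction kit, the tubes or the laboratory can form a large part of what is sequenced. A study separates that background from real signal by processing material that never touched the patient. The plan names none: no extraction blank, no-template control, blank tube or unused swab. Its one reference material is a swab that has touched skin, so its extract mixes skin, swab-material and reagent DNA with no means of telling them apart.

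Two errors could follow. Reagent taxa that survive subtraction could be read as CSF findings. An organism truly in the CSF that also lives on skin could be subtracted away. With the rule undefined, the balance between these errors could also be settled after the results are seen.

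**Working it through.** **Nothing to reproduce.** The documents give no figure for contamination, microbial DNA, read depth or the microbiome analysis. The arithmetic below is illustrative, and every copy number, depth and threshold in it is an assumption.

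**Step 1. Which controls are stated.** Sections 4 (Diagnostic work-up), Collection and processing of samples, and Statistical methods and analysis plan were compared. Swab subtraction is the only contamination control specific to sequencing. Sterile tubes and accredited processing are general measures, and section 2 (Study setting) describes the accreditation as that of a specialist immunology laboratory.

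**Step 2. How much of a CSF sample could be reagent DNA, before any subtraction.** With R reagent copies and T true microbial copies, reagent share = R / (R + T).

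| R | T = 10 | T = 100 | T = 1,000 | T = 10,000 |
|---|---|---|---|---|
| 10 | 50% | 9.1% | 1.0% | 0.1% |
| 100 | 90.9% | 50% | 9.1% | 1.0% |
| 1,000 | 99.0% | 90.9% | 50% | 9.1% |

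For example, 100 / (100 + 10) = 90.9%. Reagent DNA is the majority only when T is smaller than R, and the documents do not say whether that is so.

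The share also depends on T. If diagnostic groups differ in true microbial DNA (assumption), the reagent share differs between them even with identical reagents: at R = 100, 90.9% at T = 10 against 9.1% at T = 1,000.

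**Step 3. Could swab subtraction remove the reagent taxa?** Suppose the swab goes through the same kit and so also carries R reagent copies, spread equally over 20 taxa, along with K skin copies, and is sequenced to 50,000 reads. Each reagent taxon then has relative abundance f = R / (R + K) / 20, and the chance that it shows at least one read is 1 − (1 − f)^50,000.

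| K (skin copies) | R = 10 | R = 100 | R = 1,000 |
|---|---|---|---|
| 1,000 | about 100% | about 100% | about 100% |
| 10,000 | 91.8% | about 100% | about 100% |
| 100,000 | 22.1% | 91.8% | about 100% |
| 1,000,000 | 2.5% | 22.1% | 91.8% |

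For example, with R = 100 and K = 1,000,000, f = 100 / 1,000,100 / 20 = 0.000005 and the chance is 22.1%.

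These chances apply to a rule that deletes any taxon with a single swab read. If deletion instead requires 0.1% relative abundance on the swab, a reagent taxon is removed only when f is at least 0.001. That holds in three of the twelve cells: R = 100 with K = 1,000, and R = 1,000 with K = 1,000 or 10,000. At 100,000 or more skin copies no reagent taxon is removed for R up to 1,000.

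**Step 4. What the rule does to true organisms.** The single-read rule catches most reagent taxa but also deletes any CSF organism seen on the skin. The 0.1% rule, on a swab with a heavy skin load, deletes the organisms common on skin and leaves the reagent taxa. A model that compares amounts in swab and sample need not do either. The result turns on a choice that the plan does not make.

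**The case against.** The strongest reply has four parts.

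**The swab may catch some reagent DNA.** If it is extracted with the same kit, it carries the same reagent taxa, and subtraction would remove some of them. This stands. A reader might infer that swab subtraction cannot remove reagent DNA at all; Step 3 shows that removal is unreliable and rule-dependent, not impossible.

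**Deletion of true organisms assumes a rule.** The plan says only that background is subtracted. This also stands: such deletion is a possibility, and the firm defect is that the rule is undefined.

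**The setting may not be as low in DNA as suggested.** The remark on sterility explains why finding acid-fast bacilli is informative; it does not describe this cohort. Under section 3 (Inclusion and exclusion criteria) the sample includes bacterial meningitis and TBM. The blood samples are also covered by the swab step. So a reader might infer that the CSF microbiome results will be mostly artefact, but no DNA amount in the documents supports that. The documents do still indicate that CSF generally holds little microbial DNA.

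**Laboratory procedures may already include blanks.** They may, and silence does not prove omission. But the quality statement names no sequencing control, and the plan does state how background is to be handled: by skin subtraction. That stated step is what needs changing.

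A further inference would be that study dates from November 2016 to December 2025 imply changing kit lots and hence a false difference between TBM and other children. The documents do not say when, in what batches or with which kits DNA is extracted, and no microbiome comparison between groups is specified. That inference is not supported.

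**Conclusion.** The concern holds in limited form. Used-swab subtraction is the only sequencing-specific contamination control stated. It is not designed to measure reagent, tube or laboratory DNA, cannot be relied on to remove it from CSF with little microbial DNA, and may remove true organisms shared with skin.

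The size is unknown. The range of 0.1% to 99% rests wholly on assumed amounts (10 to 1,000 reagent copies, 10 to 10,000 true copies) and describes reads before subtraction, so it is not an estimate of what remains afterwards.

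The consequence is confined to an exploratory component. The biosignature and RNA aims (1-3) and the point-of-care test (aim 5) do not use sequencing data, and aim 4 as listed does not mention the microbiome. The change is worth making before extraction begins, but the main diagnostic aims do not depend on it.

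**What to change.** In section 4 (Diagnostic work-up) and in Collection and processing of samples:

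1. Carry an extraction blank and an unused alcohol swab through extraction and sequencing with every batch.
2. Mix TBM and non-TBM samples within each batch, so that any batch difference is not aligned with diagnosis.
3. Identify contaminants by comparing each taxon's prevalence in blanks with its prevalence in samples, under a rule fixed in advance.
4. Use the used-swab profile to flag possible skin carry-over, not to delete taxa automatically. Presence on the swab shows that an organism was on the skin, not that it entered the sample.
5. Report results with and without swab subtraction.
6. Add a short microbiome paragraph to the analysis plan and reconcile the aim 4 reference with the list of aims. The same section also cites aims 6 and 7, although the list ends at 5, so the numbering there needs checking as a whole.

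The cost is a few wells per run, hence slightly fewer patient samples per run, and a little more analysis. No extra patient sample is needed. Blanks should be specified before extraction, since a batch already processed without them may not be recoverable.
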